1. SUMMARY OF THE STUDY

According to the Tokyo 2018 acute cholecystitis diagnosis and treatment guideline, there is currently no definite conclusion about when patients diagnosed with Grade II acute cholecystitis should be operated on. In this study, two different treatment methods, which have been applied before in the literature and whose superiority has not been clearly proven, will be compared. The patients will be operated in the early (first 7 days) and late (>6 weeks) periods and the difference between the two groups in terms of difficult cholecystectomy, mortality and morbidity will be compared.

2. PURPOSE OF THE STUDY

Acute cholecystitis is a gallbladder pathology that can lead to serious complications, and Tokyo 2013 and 2018 acute cholecystitis and acute cholangitis diagnosis and treatment guidelines have been published in order to be applied in the diagnosis phase. In these guidelines, patients were divided into three groups based on clinical findings, laboratory findings, and imaging findings, and these groups were named as Grade I, Grade II, and Grade III. While early cholecystectomy is recommended in Grade I patients, treatment options such as early cholecystectomy, late cholecystectomy after antibiotic therapy, and late cholecystectomy after cholecystostomy are left to the discretion of clinicians in Grade II high-risk and Grade III patients, depending on the clinical condition of the patient. Although there is no definite opinion about which treatment is superior today, the studies included patients in all three stages. In addition, most of the studies in the literature have been carried out retrospectively, and the number of prospective studies is very few. In this study, we will examine whether there is a significant difference in terms of difficult cholecystectomy, mortality and morbidity between early and late cholecystectomy in Grade II patients who are most difficult in the decision stage.

Koetsu Inoue et al. reported that there are fewer technical difficulties in cholecystectomies performed within the first 96 hours after admission with the diagnosis of acute cholecystitis (1).

In contrast, Yun-Xiao Lyu et al. showed that there is a significant difference between cholecystectomy performed at the first admission and cholecystectomy performed in the late period, only in terms of length of hospital stay (2). Ismael Mora-Guzmán et al. also reported in their study that there was no significant difference in complications between early and late cholecystectomy(3). Again, Vinoban Amirthalingam et al. It has been reported that early period cholecystectomy can be performed safely in Grade II and III patients (4). In all these studies, no clear distinction was made for early and late cholecystectomy, and both techniques were shown to be applicable.

3. EXPECTED BENEFITS AND RISKS FROM THE RESEARCH

In this study, there is no expected risk since a different treatment method and medication will not be tried in previous similar studies. As a result of this study, if there is a difference between the research groups, new data will be obtained in terms of the approach to Grade II acute cholecystitis in the literature. Due to the limited number of prospective studies on this subject, the data to be obtained may change the treatment scheme to be applied in the future for the patient population in the research group and may benefit from reducing the complication rates.

4. TYPE, SCOPE, DESIGN AND THE DATA TO BE OBTAINED AFTER THE RESEARCH STATISTICAL TO BE USED IN THE EVALUATION METHODS

The research was planned as a prospective study. The study is single-centered and the patient group graded as Grade II according to the Tokyo 2018 guideline acute cholecystitis diagnostic criteria will be included in the study. Grade I and III patients, patients with accompanying choledocholithiasis, patients who are pregnant or likely to become pregnant, patients who cannot comply with the treatment due to their mental status and who cannot sign their own consent for treatment will not be included in the study. Patients classified as Grade II acute cholecystitis will be informed about the treatment options and possible complications after hospitalization. Patients will decide on the treatment method to be applied with their consent. The patients will be divided into two groups as those operated in the early period (first 7 days) and those operated in the late period (>6 weeks). The parameters to be compared were the rate of conversion from laparoscopic to open, bile duct injury and bile leakage rate, grade II-III complication rate in the Clavien Dindo complication scoring system, morbidity rate in the first 30 days postoperatively, and difficult cholecystectomy rate based on intraoperative imaging findings according to the Parkland scoring system. The research will be terminated when the number of 120 patients determined by the power analysis result is reached.

Chi-square and Student's t test will be used for the statistical evaluation of the results of the patients, respectively, for quantitative and continuous variables, and Mann-Whitney U test (two samples) or Kruskal-Wallis test (more than two samples) will be used for the analysis of abnormally distributed variables.

5. THE NUMBER OF PATIENTS AND VOLUNTEERS TO BE INCLUDED IN THE RESEARCH QUALITY AND JUSTIFICATION OF SELECTION (AGE RANGE, GENDER ETC.).

The research population was determined as 120 patients as a result of the power analysis results. The number of volunteers will be 120, and the patient group graded as Grade II according to the Tokyo 2018 guideline acute cholecystitis diagnostic criteria will be included in the study, regardless of gender group over the age of 18.

6. PARAMETERS TO LOOK AT AND WHERE TO LOOK AT THE PARAMETERS AND BY WHOM

Parameters to be checked: Age, gender, comorbid diseases, previous abdominal operations, drug allergy, ASA score, Parkland score, length of hospital stay, duration of operation, amount of bleeding during the operation, type of operation, biliary tract complication, Clavien Dindo complication score, postoperative mortality and morbidity. The parameters will be checked and recorded by the principal investigator during the application and follow-up.

7. WHICH PARAMETERS TO BE USED IN THE RESEARCH ARE ROUTINE FOR THAT DISEASE GROUP AND WHICH ARE SPECIALLY REQUESTED FOR THE RESEARCH

Among the parameters and tests used in the research, there are no specific ones used for the research, and all of them are recorded and requested during the routine follow-up of the disease.

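### Patients choose early or late surgery, but only unadjusted tests are planned, so a crude difference may reflect case mix rather than timing

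*Combined protocol and SAP*

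**What the plan says.** Section 4 describes a prospective single-centre study in which patients are informed of the options and then choose: "Patients will decide on the treatment method to be applied with their consent". Groups are formed by the timing of surgery, within 7 days or after more than 6 weeks. Neither randomisation nor matching is mentioned anywhere.

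Entry is restricted. Section 4 excludes, among others, "Grade I and III patients, patients with accompanying choledocholithiasis".

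For the analysis, Section 4 says that chi-square and Student's t tests "will be used for the statistical evaluation of the results of the patients, respectively, for quantitative and continuous variables", and names the "Mann-Whitney U test (two samples) or Kruskal-Wallis test (more than two samples") for variables that are not normally distributed. No regression, stratified or propensity-score analysis appears in any section.

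Section 6 lists baseline items to be recorded, including "Age, gender, comorbid diseases, previous abdominal operations, drug allergy, ASA score". It gives them no role in the comparison of the groups.

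Section 2, describing the guidelines, says that the treatment options "are left to the discretion of clinicians in Grade II high-risk and Grade III patients, depending on the clinical condition of the patient". Section 3 expects that "the data to be obtained may change the treatment scheme to be applied in the future".

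**The concern.** The aim is to learn whether operating early or late changes surgical difficulty, mortality and morbidity, and Section 3 foresees the answer influencing practice. That is a causal use of the comparison. It requires groups that are alike apart from timing, or an analysis that allows for the ways in which they differ.

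The plan provides neither. Restricting entry to one severity grade removes some differences, but patients within Grade II still vary in age, ASA score, comorbidity and surgical history. Section 2 itself recognises a high-risk subgroup within Grade II and ties the treatment option to clinical condition. If sicker or frailer patients lean towards one timing, the crude tests will credit or blame timing for what those patients brought with them. The bias could run in either direction, and a larger sample would not remove it.

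**Working it through.** **The plan's own figure.** The only number is the total of 120 patients (Sections 4 and 5). No alpha, power, effect size, event rate or group split is stated, so it cannot be reproduced. If the split were 60/60 with a two-sided 5% test and 80% power, 120 would fit differences of about 20.5 to 25.5 percentage points (lower rate 10-50%, no continuity correction). This gives a scale for the spurious differences below.

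**Step 1: bias under no timing effect.** Assume one binary risk factor with outcome risk p_H in high-risk and p_L in low-risk patients, and high-risk shares q_1 and q_2 in the two groups. The expected risk in group k is

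r_k = q_k × p_H + (1 − q_k) × p_L,

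so the spurious difference is r_1 − r_2 = (q_1 − q_2) × (p_H − p_L). For example, with shares of 50% and 20% and risks of 50% and 20%, it is (0.50 − 0.20) × (0.50 − 0.20) = 0.09, or 9 points.

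**Step 2: false-positive rate of the crude test.** The uncorrected chi-square statistic is

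X² = (x_1/n_1 − x_2/n_2)² / [p̄(1 − p̄)(1/n_1 + 1/n_2)], with p̄ = (x_1 + x_2)/(n_1 + n_2).

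The rate is the sum of the two binomial probabilities over all outcome pairs with X² > 3.841. With p_H = 50% and p_L = 20% (all inputs assumed):

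| High-risk shares (groups 1, 2) | Expected risks | Spurious difference | 60/60 | 90/30 | 30/90 |
|---|---|---|---|---|---|
| 35%, 25% | 30.5%, 27.5% | 3 points | 6.8% | 5.7% | 6.8% |
| 40%, 20% | 32%, 26% | 6 points | 11.6% | 8.5% | 10.9% |
| 50%, 20% | 35%, 26% | 9 points | 19.3% | 13.7% | 17.2% |
| 60%, 20% | 38%, 26% | 12 points | 29.6% | 21.1% | 25.6% |

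With no imbalance the rate is 5.1-5.3%.

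**Step 3: other outcome risks, 60/60, same shares.** Risks of 30% and 10% give spurious differences of 2-8 points and rates of 5.7-20.2%. Risks of 6% and 2%, standing for rare outcomes, give 0.4-1.6 points and 3.9-6.2%.

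**Step 4: what adjustment recovers.** A Mantel-Haenszel test stratified on the risk factor (60/60, risks 50% and 20%, 100,000 simulated trials) rejects 4.9-5.0% of the time if the factor is measured perfectly, which is true by construction. The rate is about 5-9% if 10% of patients are misclassified and about 6-16% if 20% are.

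**Step 5: cost and feasibility at N = 120.** Logistic regression was simulated with no timing effect and assumed covariate effects on choice and outcome (1,500 trials per setting). At baseline event risks of 10-30%, crude models rejected 7-15% of the time and adjusted models 4-6%. The standard error was 10-12% larger with 3 factors, 13-14% with 5 and 20-22% with 10. At a baseline risk of about 3%, 40%, 51% and 56% of fits with 3, 5 and 10 factors failed or were unstable. These figures depend on the assumed effects and are indicative only. They support few covariates, and regression only where events are not rare.

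**The case against.** The strongest objection is that the link between choice and risk is inferred. The Section 2 sentence describes what the guidelines leave to clinicians, covers Grade III as well, and includes drainage among the options; in this study the patient decides. The documents never say that patients choose according to risk. This stands as a limit on what can be claimed. It does not remove the problem, because patients decide after being told about options and complications, and nothing in the design prevents that choice from following their condition.

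Second, the generic tests in Section 4 could be applied to the baseline items in Section 6, so those items need not go unused. That is fair: what the plan lacks is an adjusted analysis. A baseline comparison would show imbalance on recorded factors but would not correct the outcome comparison.

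Third, every magnitude is assumed. The mildest imbalance gives only 5.7-6.8% for the non-rare outcomes shown, and for rare outcomes at a 90/30 split the crude rate falls below 5% (1.2-2.4%). The concern about p-values therefore applies mainly to the commoner outcomes.

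Fourth, adjustment is only a partial cure. Severity within Grade II may be the main driver of choice, and it is not in the Section 6 list. This also stands. In the same scenarios, though, adjustment with 20% misclassification leaves at most about 16%, against 29.6% for the crude test.

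**Conclusion.** The concern holds and should be fixed before the results are interpreted. Treatment is self-selected, every planned test is unadjusted, and the intended use is causal. Under the stated assumptions (no timing effect, two-sided 5%, one binary risk factor, 60/60), spurious differences of 2-12 points and false-positive rates of 5.7-29.6% arise for the non-rare outcomes, while inflation is small for rare ones. These are illustrations, not estimates: the documents give no event rates, group split, alpha or information on how choice relates to risk. The direction and actual size of any bias cannot be known from them.

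**What to change.** Amend Section 4 as follows.

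- **Design.** Describe the study as a non-randomised comparison and include a table of baseline factors by group.
- **Main analysis.** For difficult cholecystectomy by Parkland score, 30-day morbidity and Clavien-Dindo grade II-III complications, make an adjusted early-late comparison the main result.
- **Covariates.** Prespecify age, ASA score and previous abdominal operations, adding comorbidity only if event counts allow under a rule fixed in advance. Do not adjust for the Parkland score, which is an outcome.
- **Method.** Use regression when events reach a stated cut-off, and a propensity score on the same factors below it. A possible cut-off is 20 events: four model terms (timing plus three factors, with ASA as one term) × 5 events each. This is a convention, not a figure from the documents. Conversion and bile leakage follow the same rule.
- **Rare outcomes.** For bile duct injury and mortality, report crude rates with exact intervals, or a propensity-adjusted estimate if counts allow, and label them descriptive.
- **Crude tests.** Keep them as secondary.
- **Limitation.** State that unmeasured confounding remains, including severity within Grade II.

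The cost is wording and modest analysis work. The named factors are already to be recorded, so no new data capture is needed. Intervals would be somewhat wider: about 10-12% in standard error with three factors in the simulation above. Recording severity at admission and symptom duration would strengthen the adjustment, but that would be additional data collection.

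### The groups are worded by when the operation took place and no outcome is defined for the waiting period, so the promised mortality and morbidity comparison can miss harm during the delay

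*Combined protocol and SAP*

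**What the plan says.** **Allocation and groups.** Section 4 leaves the choice of treatment to the patient after admission: "Patients will decide on the treatment method to be applied with their consent". In the next sentence the patients are to be "divided into two groups as those operated in the early period (first 7 days) and those operated in the late period (>6 weeks". Section 1 uses the same two windows.

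**Aim.** Section 1 says that "the difference between the two groups in terms of difficult cholecystectomy, mortality and morbidity will be compared". Section 2 states the aim in similar terms: "mortality and morbidity between early and late cholecystectomy in Grade II patients".

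**Outcomes.** In Section 4's list of compared parameters, the only item with a stated period is "morbidity rate in the first 30 days postoperatively". Mortality is not on that list. Section 6 lists the recorded items, among them "type of operation, biliary tract complication, Clavien Dindo complication score, postoperative mortality and morbidity". On timing it says only: "The parameters will be checked and recorded by the principal investigator during the application and follow-up".

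**Not stated anywhere.** There is no rule for patients operated between day 8 and week 6 or never operated, no intention-to-treat, per-protocol or crossover rule, and no statement of what the 7 days and 6 weeks are counted from. The chosen strategy is not a recorded item. Section 9 covers leaving or removal from the study, but not how such patients are analysed.

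**The concern.** Two gaps act on the same comparison.

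The first is who is in it. If the groups are formed from operations performed, entry to the late group depends on something that happens after the choice, namely reaching surgery after more than 6 weeks. Patients who chose delay but were operated in the gap or never operated drop out of both groups. One operated within 7 days counts as early.

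The second is when the clock starts. A patient who chooses delay is at risk for more than 6 weeks before a postoperative count begins; one who chooses early surgery is at risk for at most about 7 days. A death during the wait is not postoperative and, read literally, belongs to a patient without a group.

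The protocol describes the disease as one that can lead to serious complications, and it expects the results to influence future treatment. If harm during the delay is not counted, late surgery can look better than the choice of delay really is. If the chosen strategy and waiting-period events are not recorded as they occur, the planned tests cannot recover them.

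**Working it through.** **Check of the text.**
- *What defines a group?* Section 4 gives patient choice in one sentence and operation performed in the next. Nothing says which governs.
- *Where do gap and non-operated patients go?* With as-operated groups, nowhere. With planned-timing groups, to the group they chose, but the plan does not say so and does not record the choice.
- *Which outcomes could register harm during the wait?* Conversion, Parkland difficulty, and bile duct injury and leakage arise from the operation. Section 4 morbidity and Section 6 mortality and morbidity are postoperative. Length of stay, biliary tract complication and Clavien-Dindo score have no time origin and might catch some events. No item is defined to do so.

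The plan gives no figure to reproduce here. Its total of 120 plays no part, and its power inputs are not reported.

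**Illustration for morbidity. Every rate is an assumption.**
- Postoperative morbidity is 15% under both strategies, independent of waiting events.
- *w* = share of delay-choosers with a complication in a 42-day wait: 5, 10 or 20%.
- *e* = share of early-choosers with one in 7 preoperative days at the same daily risk: 1 − (1 − *w*)^(7/42) = 0.85, 1.74 or 3.65%.
- *c* = share of waiting events that the Section 6 items happen to pick up.
- *g* = share of patients with a waiting event who are operated before week 6 or never. They are removed from the late group; the model does not add any to the early group.

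Counted from the decision:
- Delay: 1 − 0.85(1 − *w*) = 19.25, 23.50, 32.00%.
- Early: 1 − 0.85(1 − *e*) = 15.72, 16.48, 18.10%.
- Difference: 3.53, 7.02, 13.90 points.

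As the plan would show it:
- Late: 1 − 0.85(1 − *c*·*w*(1 − *g*)/(1 − *w*·*g*)).
- Early: 1 − 0.85(1 − *c*·*e*).

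Hidden amount = difference from the decision minus the difference shown, in percentage points:

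| *c* | *g* | *w* = 5% | *w* = 10% | *w* = 20% |
|---|---|---|---|---|
| 0 | any | 3.53 | 7.02 | 13.90 |
| 0.5 | 0 | 1.76 | 3.51 | 6.95 |
| 0.5 | 0.5 | 2.80 | 5.52 | 10.73 |
| 1 | 0 | 0 | 0 | 0 |
| 1 | 0.5 | 2.07 | 4.03 | 7.56 |

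With *c* = 0 the plan shows 15% against 15%. The row *c* = 1, *g* = 0.5 shows that complete recording alone does not close the gap if groups are formed as operated. In the extreme corner *c* = 1, *g* = 1, the hidden amount is 4.25, 8.50 or 17.00 points, because early events count and no delayed patient with an event remains in the late group. If preoperative risk falls mainly in the first 7 days under both strategies, *e* approaches *w* and the difference from the decision tends to 0.

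**Illustration for operative endpoints, also assumed.** Take a 30% difficult rate among patients reaching late surgery, a share *f* = 10, 20 or 30% of delay-choosers operated in the gap, and a difficult rate *q* among those. The rate in all operated delay-choosers differs from 30% by *f*(*q* − 30%):
- *q* = 20%: −1, −2, −3 points (late rate overstated).
- *q* = 30%: 0.
- *q* = 50%: 2, 4, 6 points (late rate understated).
- *q* = 70%: 4, 8, 12 points (late rate understated).

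The sign turns on *q*, which the documents do not give.

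**Follow-up, taking the treatment decision as time zero (an assumption).** Late surgery falls after day 42, so 30 postoperative days end after day 42 + 30 = 72. For early surgery they end by day 7 + 30 = 37. The extra follow-up for early-choosers is at least 72 − 37 = 35 days. Counting 72 days back from the end date in Section 8, 14.06.2021, gives 03.04.2021.

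**The case against.** The strongest reply is that the choice sentence stands directly before the grouping sentence and that Section 1 is written prospectively, so the investigators may have meant groups by planned timing. That is a fair reading. A reader might infer from the grouping sentence alone that the late group is certainly selected on completing the wait; the documents do not support that certainty. They do not settle the matter the other way either, and the planned-timing reading leaves the waiting-period outcome undefined.

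A second reply is that the study compares operations rather than strategies. Most items in Section 4's compared list concern surgery, and for that question as-operated groups and a postoperative clock are coherent. This stands for the operative endpoints. It does not dispose of mortality and morbidity, which Sections 1 and 2 promise without limiting them to the postoperative period, while Section 1 speaks of comparing treatment methods.

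A third reply is that recording during admission and follow-up may catch waiting events. It may, through the three items without a time origin, so it would be wrong to infer that all such events are lost. Capture is left to chance, however, and does not restore patients who leave the late group.

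Finally, every rate above is assumed, and the hidden amount can be zero. That stands.

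**Conclusion.** The point holds as a defect in the grouping rule and the outcome clock, not as a demonstrated bias of known size. As worded, gap and non-operated patients have no group; if planned timing was meant, that part shrinks. Under either reading, no item is defined for complications or deaths during the wait, and mortality is missing from Section 4's compared list.

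The mortality and morbidity comparison would favour late surgery if harm occurs during the delay and goes uncounted. With waiting-complication rates of 5–20%, equal daily risk and 15% postoperative morbidity, the main illustration hides 0 to about 14 points, with 17 only in the extreme corner noted above. None of these rates comes from the documents.

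A reader might infer that the operative endpoints are also tilted towards late surgery. That is not supported: the direction depends on how difficult the gap operations are. Nor can a net bias be given that allows for early-choosers slipping past day 7, because it would need the difficult rate in early patients operated on time, which the documents do not state.

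This should be settled before the analysis, because it decides who is analysed and from when events count.

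**What to change.** **Section 4.** Record the strategy chosen at the treatment decision and make the main comparison by that choice. Analyse operative endpoints in all operated patients of the chosen group, whatever the day of surgery. Alongside, keep the as-operated comparison (first 7 days against more than 6 weeks) and the 30-day postoperative morbidity rate, and tabulate chosen strategy by actual timing: first 7 days, day 8 to week 6, more than 6 weeks, not operated. State what the 7 days and 6 weeks are counted from.

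**Section 6.** Add the chosen strategy, and complications and deaths during the wait. Count mortality and morbidity by chosen group from the decision to one pre-specified common time point that covers 30 days after late surgery, including patients never operated. If the wait is counted from the decision, that point lies beyond 72 days. It should be set from the site's actual waiting times, because the late window has no upper limit.

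**Cost.** Two added data items, some dilution of the timing contrast, follow-up of gap and non-operated patients, and at least about 35 more follow-up days for early-choosers. Section 7 calls only the listed parameters routine, so if the centre's records do not hold waiting-period events, collecting them takes extra effort. The last enrolment date moves earlier or the end date moves later; 03.04.2021 is a best case only. Confounding by patient choice remains. How patients who do not complete the wait are managed clinically is for the investigators to state.

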9. WITHDRAWAL AND TERMINATION CRITERIA

When patients want to leave the study, they can leave the study provided that they inform the principal investigator. The research doctor, who is also the coordinator of the study, may remove the patient from the study without informing the patient due to my negligence in fulfilling the requirements of the study program or in order to improve the quality of the medical care I am receiving.

The research will be terminated if the determined population (even earlier than the determined date) is reached.

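### The Clavien-Dindo comparison in Section 4 stops at grade III and has no time window, so read literally it scores a patient whose only complication is grade IV or V as a non-event

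*Combined protocol and SAP*

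**What the plan says.** Section 4 divides patients into "those operated in the early period (first 7 days) and those operated in the late period (>6 weeks") and lists the outcomes on which the groups will be compared. One is the "grade II-III complication rate in the Clavien Dindo complication scoring system". The next is the "morbidity rate in the first 30 days postoperatively". The 30-day limit is attached only to that second item, and morbidity is not defined anywhere.

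Section 6 lists the data to be collected, among them "Clavien Dindo complication score, postoperative mortality and morbidity". The score is recorded there with no grade limit. On timing, Section 6 says only this: "The parameters will be checked and recorded by the principal investigator during the application and follow-up".

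Section 1 states that "the difference between the two groups in terms of difficult cholecystectomy, mortality and morbidity will be compared", and Section 2 repeats the aim: "we will examine whether there is a significant difference in terms of difficult cholecystectomy, mortality and morbidity". Mortality is therefore a stated comparison, although Section 4's list does not name it.

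**The concern.** A complication rate should not improve when outcomes get worse. One that is closed at grade III can do so in two ways, taking the standard scale as an assumption because the documents do not describe the grades.

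- A patient whose only complication is grade IV or V is not in the numerator.
- If patients are scored by their highest grade, one who worsens from III to IV leaves the numerator. The plan does not say whether scoring is by highest grade or by any qualifying event, so the same data can give two different rates.

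This is the only severity-graded complication comparison in Section 4's list. The 30-day morbidity rate may catch some grade IV-V patients, but it does not show how severe their complications were.

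The missing window is a second gap in the same item. Without a fixed period after surgery, the rate depends on how long each patient happens to be observed.

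**Working it through.** **Figure to reproduce.** The plan gives no event rate, group size or power statement for this outcome. The total of 120 (Sections 4 and 5) is attributed to a power analysis whose inputs are not stated, so it cannot be tied to this outcome. The check is therefore a reading of the rule, followed by an illustration with assumed counts.

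**How the written rule scores a patient** (standard scale assumed):

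| Patient's complications | Highest-grade scoring | Any grade II-III event counts | Grade II or higher |
|---|---|---|---|
| II or III only | event | event | event |
| III, then IV | non-event | event | event |
| IV or V only | non-event | non-event | event |

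The last row is a non-event under both counting rules. The middle row depends on a rule that the plan does not state.

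**Shift per uncounted patient.** This is 1/n for a group of n. Group sizes are assumed, because patients choose their treatment and no split is given: 1/60 = 1.7 points, 1/90 = 1.1 points, 1/30 = 3.3 points.

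**Effect on the comparison.** Let e be the number of uncounted patients in a group. Then:

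literal difference = (difference in grade II or higher) − (e₁/n₁ − e₂/n₂)

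If the uncounted proportion is the same in both groups, the difference does not move. Otherwise the group with the larger uncounted proportion looks better than it should.

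**Illustration with assumed counts.** Both groups truly have 8/60 = 13.3% at grade II or higher: difference 0.0 points, Newcombe 95% CI −12.6 to 12.6. Now let 1, 2 or 3 of the 8 patients in one group go uncounted. The difference below is that group minus the other, and p is from the uncorrected chi-square test.

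| Uncounted | Literal rates | Difference (points) | 95% CI | p |
|---|---|---|---|---|
| 1 | 7/60 = 11.7% vs 13.3% | −1.7 | −14.0 to 10.7 | 0.78 |
| 2 | 6/60 = 10.0% vs 13.3% | −3.3 | −15.4 to 8.7 | 0.57 |
| 3 | 5/60 = 8.3% vs 13.3% | −5.0 | −16.8 to 6.7 | 0.38 |

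If these patients had a III that worsened to IV, the table holds only under highest-grade scoring; if any II-III event counts, every shift is zero. If their only complication was IV or V, it holds under both rules.

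With an assumed 90/30 split, a true rate of 13.3% in each group and 2 uncounted patients, the shift is 2/30 = 6.7 points if they are in the smaller group (2/30 vs 12/90; CI for the difference −16.5 to 9.0). It is 2/90 = 2.2 points if they are in the larger group (10/90 vs 4/30; CI −19.3 to 9.2).

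**Will such patients occur?** At assumed overall grade IV-V rates of 1%, 2% and 5%, the chance of at least one among 120 is 1 − 0.99¹²⁰ = 70%, 1 − 0.98¹²⁰ = 91% and 1 − 0.95¹²⁰ = 99.8%.

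**The case against.** The strongest reply is that the consequence is small and partly covered. This is one of five listed comparisons, and none is designated primary. II-III may simply be loose wording. A grade V patient counts under the mortality aim of Sections 1 and 2, and a grade IV patient within 30 days plausibly counts as morbidity. Everything needed for a correct analysis is recorded under Section 6. All of this stands, and it limits the seriousness of the point. It does not repair the item, because no section says that the comparison extends above grade III.

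It can also be said that the illustration rests on assumed counts, that part of it depends on highest-grade scoring, and that every interval includes zero. That is correct. The illustration shows what the rule can do to an estimate. It does not show that this will happen, and it shows no effect on significance.

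Two stronger readings are tempting, and the documents support neither.

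- A reader might infer that grade IV-V events drop out of the study. They do not, since Section 6 captures them.
- A reader might infer from Section 9 ("The research will be terminated if the determined population (even earlier than the determined date) is reached") that late patients, operated on weeks after early ones, will have less time for complications to be recorded. That needs a common close date that cuts off follow-up, and no section states one. The missing window is a fact; unequal follow-up between the groups is not established.

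**Conclusion.** The point holds as a defect of definition and should be fixed before any comparison between groups. As written, the item scores a patient whose only complication is grade IV or V as a non-event, leaves the per-patient counting rule open and has no time window. Confidence is high on how the rule scores such patients, given the standard meaning of grades IV and V.

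The size and direction of any bias cannot be derived: the documents give no event rates or group sizes, and the uncounted patients could fall in either group. The per-patient shift of 1.7 points in a group of 60 (1.1 in 90, 3.3 in 30) is a scale for judging the effect, not an estimate of it. That mortality is absent from Section 4's list is a minor inconsistency with Sections 1, 2 and 6; the list may not have been meant as exhaustive.

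**What to change.** In Section 4, replace the Clavien-Dindo item with: proportion of patients whose highest Clavien-Dindo grade within 30 days after surgery is II or higher (II-V). This settles the threshold, the counting rule and the window in one sentence, and it uses the 30 days already set for morbidity. Add a descriptive table of highest grade (none, I, II, III, IV, V) by group. Add postoperative mortality to Section 4's list so that it agrees with Sections 1, 2 and 6. Section 2 can stay as it is.

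The cost is two edits to one sentence and one table. No new outcome variable is needed, and 30-day follow-up is already required for the morbidity rate.

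There are three downsides:

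- The outcome mixes moderate and severe events. The grade table offsets this.
- It will overlap with the 30-day morbidity rate.
- A window counted from surgery leaves out complications during the late group's wait of more than 6 weeks. Report these separately.

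The documents do not settle which threshold was intended. If the sponsor means a different one, such as III or higher, the same form of words applies: highest grade per patient, no upper limit, and a fixed window.
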